**Stage 3 Procedures:**

*Intervention: FMI Mini-Controlled Trial with Intensive Follow-Up*

In this stage, we will test the finalized FMI (see **Screening, Eligibility, and Recruitment** above). To do this, we will contrast outcomes among those in this trial (N=24 dyads) with 24 pairs of friend dyads (total dyad N=48) who are randomly assigned to a wait list control condition.

The FMI will consist of a single session. Sessions will be offered on many days and times across the week to accommodate variability in student schedules. Each session will begin with a baseline assessment. In this session, women will be provided with the refined intervention protocol and will have the opportunity to role play and practice implementing the skills and strategies. Following the intervention, participants will be encouraged to utilize the skills and strategies presented in the intervention over the next 12 weeks, whenever they are out with their friend in a social context.

Dyad pairs assigned randomly (stratified on drinking levels, sexual assault history, and age) to the wait list control condition will be assessed once at baseline and again 12 weeks post-baseline. Assessment measures (baseline, 12 weeks) will mirror those administered to women in the FMI condition. At the completion of the 12 week “wait list,” participants will be administered the FMI and followed for 12 weeks. Comparison of outcomes across conditions will allow for stronger inferences about the efficacy of the intervention, will allow for examination of measurement reactivity, and will increase our sample size to examine within person change.

*Follow-up Assessments.* We will conduct bi-weekly online post-intervention assessments (with the first assessment to occur within 2 weeks of FMI completion) for 12 weeks. The bi-

weekly structure will optimally capture women's experiences applying strategies from the intervention. Participants will be reminded of follow-up assessments by phone, text, and email prompt. Individual members of the dyad will be interviewed in the unlikely event that the other member is lost to follow up over the brief follow-up period. At the end of the 12 weeks, participants will be contacted for an exit interview.

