## Statistical Analysis Plan

*Data preparation.* We will examine patterns of missing data, research dropout rates, therapist adherence and competence, distributional properties of our measures, and correlations among outcome measures. Though we expect some missing data due to attrition, this will be minimal given the short follow-up, the focus on close friend dyads, and employment of rigorous participant retention procedures that have proven effective in our prior work. Importantly, our analytic approach (below) will allow us to include cases with missing data. In the case of one friend dropping out, we will attempt to determine whether the intervention played any role in study attrition. We will examine for FMI and control group differences on baseline measures and demographics, and if differences emerge, we will include the relevant variables as covariates in analysis.

*Treatment Feasibility and Fidelity.* Descriptive analyses of adherence data, refusal rates, follow-up rates, and participant evaluations will be used to guide possible changes in the intervention and to provide information on feasibility and acceptability. Decisions about possible intervention changes will be made with consideration of qualitative data (analysis described above) and investigator input. As noted, we will collect data on fidelity to ensure that the FMI was administered according to protocol and consistent with MI spirit.

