A prominent feature of our design is that individuals are nested within dyads, and this necessitates a data analytic approach that can accommodate nested data structures. Hence, our Aim 3 analyses are built around hierarchical linear models (HLMs). First, we will evaluate group differences on variables from our first post-intervention assessment (i.e. perceived barriers, readiness, alcohol knowledge and strategies, and implementation of FAPBs) using a two level model (individuals nested within dyads). Treatment will be dummy coded (FMI vs. waitlist control group) and included as a level two covariate. Second, we will utilize all data from our three month follow-ups and repeat these analyses using a three-level model (6 repeated measures nested within individuals, and individuals nested within dyads). In these models treatment will be included as a level three covariate. We will use  $\beta$  to describe effect sizes (Cohen, 1988; Selya et al., 2012).

Our burst design provides a rich opportunity to examine whether changes in target constructs of interest (e.g., barriers, skills, alcohol knowledge and strategies) are associated with implementation of FAPBs. For these analyses we will combine the post-intervention data from our FMI and WLC groups after the latter has completed the intervention and follow-up assessments. Combining groups will increase our sample size and provide more stable estimates of effect sizes. For these analyses we will include reports of past week protective behavioral strategies just prior to the intervention and weekly aggregates of variables of interest from our three-month follow-up yielding 7 repeated measures nested within individuals and individuals nested within dyads. Time will be included as a level-1 covariate, and we will

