examine change in readiness, perceived barriers, alcohol knowledge and strategies, and implementation of FAPBs. Effect sizes characterizing change will be computed in two ways: 1). Computing a difference score using baseline and the first follow-up divided by the standard deviation of the difference score, and 2). A difference score using baseline and the last assessment of the follow-up divided by the standard deviation of the difference score (Gibbons et al., 1993; Morris & DeShon, 2002). Individual level intercepts and slopes will be output from these models and this will allow us to examine correlations between slopes and intercepts. We expect that reductions in perceived barriers (better self-efficacy, fewer interpersonal concerns), and increases in readiness will be positively related to implementation of FAPBs. Our models will also allow us to include individual characteristics (e.g. assault history, drinking history, relationship, responsibility) to examine their association with change in perceived barriers, skill implementation, etc. (e.g., prior history of sexual assault is related to more or less change in variables our intervention is expected to impact).

In exploratory analyses, we will examine whether increases in implementation of FAPB from baseline to follow-up are associated with rates of sexual victimization. For these analyses we collapse our follow-up data into dichotomous variable indicating whether sexual victimization occurred. Using a two-level HLM (individuals nested within dyads), this dichotomous outcome will be regressed on the intercepts and slopes of FAPBs (described above). Steeper increases in FAPBs are expected to be associated with lower likelihood of sexual victimization at follow-up controlling for baseline levels of sexual victimization. Odds ratio will be used to describe the effect size. Data from stakeholder and exit interviews will be analyzed using qualitative data analytic techniques.

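### The pooled post-FMI growth models combine the immediate and delayed arms without an arm or arm-by-time term, so any arm difference in change is averaged over and can enter the slope correlations

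*Combined protocol and SAP*

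**What the plan says.** For the mechanism and within-person analyses, the SAP (Outcome analyses) states that "we will combine the post-intervention data from our FMI and WLC groups after the latter has completed the intervention and follow-up assessments". The reason given is that "Combining groups will increase our sample size and provide more stable estimates of effect sizes". Protocol section 16.1, Aim 3, has the same plan. The pooled model has 7 repeated measures within women and women within dyads. Of its terms the SAP says only "Time will be included as a level-1 covariate, and we will" then examine change in each construct. Individual intercepts and slopes are output, correlated across constructs, and later used as predictors of victimization.

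An arm term is specified elsewhere, for the earlier between-group models: "Treatment will be dummy coded (FMI vs. waitlist control group) and included as a level two covariate", and then at level three in the repeated-measures version. It is not carried into the pooled models.

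Two other statements come close. The SAP adds that "Our models will also allow us to include individual characteristics (e.g. assault history, drinking history, relationship, responsibility") may enter the pooled models, but arm is not among the examples. Under Data preparation, baseline measures and demographics are compared between groups and "if differences emerge, we will include the relevant variables as covariates in analysis".

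On timing, protocol section 4 (Stage 3 Procedures) says that dyads randomised "to the wait list control condition will be assessed once at baseline and again 12 weeks post-baseline". After the wait, "participants will be administered the FMI and followed for 12 weeks".

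**The concern.** Randomisation balances who enters each arm. It does not balance what the design then does to the delayed arm: a 12-week shift in calendar time, at least one more full assessment before the FMI, and restriction to dyads that remain through the wait. The protocol itself names measurement reactivity as something the design lets the team examine, but no model in the plan does so. Outcomes are reported per social occasion with the friend, so the period of the year may matter too.

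The pooled models are the stated route to the third primary goal of Aim 3, the potential mechanisms, and protocol section 16.2 says that the effect sizes are meant to inform future studies. If the arms change by different amounts, one pooled figure hides this. If they differ on two constructs at once, part of the correlation between slopes reflects which arm a woman was in, not a link between the constructs within women.

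**Working it through.** **The plan's own figure.** One pre-FMI report plus bi-weekly reports over 12 weeks gives 1 + 12/2 = 7 repeated measures, as the SAP states.

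**How the two arms enter the pooled model** (Stage 3 Procedures)

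| | Immediate FMI | Delayed FMI |
|---|---|---|
| Full assessments before the FMI | 1 (baseline) | at least 2 (baseline, 12 weeks) |
| FMI given | at baseline session | after the 12-week wait |
| Post-FMI follow-up | 12 weeks | 12 weeks, starting 12 weeks later |

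The count for the delayed arm is a minimum. The three-level between-group model uses six repeated measures, which would need bi-weekly wait-list data that Stage 3 Procedures does not schedule.

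**Induced slope correlation.** Inputs: two equal arms (24 + 24 dyads, 96 women), within-arm slope SD of 1, and an arm difference d in mean slope on both constructs. The documents give no d, so 0.3, 0.5 and 0.8 SD are assumptions. With within-arm correlation r, pooled r = (r + d²/4) / (1 + d²/4). If the differences run in opposite directions, the numerator is r − d²/4.

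- d = 0.3, r = 0: 0.0225 / 1.0225 = 0.022
- d = 0.5, r = 0: 0.0625 / 1.0625 = 0.059
- d = 0.8, r = 0: 0.16 / 1.16 = 0.138
- r = 0.30, same direction: 0.32, 0.34, 0.40
- r = 0.30, opposite directions: 0.27, 0.22, 0.12
- d = 0: no change

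**False-positive rate.** This was simulated with 5,000 runs per setting, 44 or 48 dyads, within-dyad correlation 0 or 0.3, true r = 0 and a nominal 5% test on total slopes.

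| d | Pooled | Slopes centred within arm |
|---|---|---|
| 0 | 5.1–6.4% | 5.0–6.4% |
| 0.3 | 5.1–6.9% | 4.9–5.9% |
| 0.5 | 7.8–10.5% | 4.5–6.6% |
| 0.8 | 25.2–27.3% | 5.1–5.8% |

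With slopes centred within arm, the mean correlation stays at about 0.00 for every d. What remains above 5% comes mostly from dyad clustering.

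**Pooled change.** With equal arms the pooled mean lies d/2 from each arm's own value: 0.15 SD for d = 0.3 and 0.40 SD for d = 0.8. As the SAP standardises it, the pooled effect size is the mean of the two changes divided by √(1 + d²/4). Changes of 0.50 and 0.30 give 0.40/√1.01 = 0.398. Changes of 0.50 and 0.20 give 0.35/√1.0225 = 0.346.

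**Precision of the added term.** The 95% half-width for an arm difference in change is 1.96 × √(2/n), where n = (N/2)/(1 + ICC). With N = 96 and ICC 0: 1.96 × √(2/48) = 0.40 SD. With N = 88 (the figure in section 16.2) and ICC 0.5: n = 29.3, giving 0.51 SD. Power for a 0.5 SD difference is about 48–69% over N 88–96 and ICC 0–0.5 (two-sided 0.05, assumed).

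**The case against.** The strongest reply is that the harm needs arms that differ in change, and nothing in the documents shows that they do. Arms are randomised with stratification on drinking, assault history and age, and both get the same single session. This stands: the harm is conditional, and its size cannot be taken from the plan.

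Second, the induced correlation of 0.02–0.06 for differences up to 0.5 SD is small beside a standard error of about 1/√93 to 1/√85, or 0.10–0.11, for a correlation in 88–96 women. It also needs both constructs to differ. This stands too.

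Third, arm is constant within a dyad. If the model has a dyad-level random slope and the output slopes are deviations from the dyad, they contain no arm difference. The SAP does not say whether the slopes are totals or deviations, so the leak is a possibility under one reading.

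Fourth, rolling Stage 3 delivery (July 2020 to June 2021 in the section 11 timeline) makes arm a blurred marker of calendar period. That weakens the calendar argument but leaves the extra assessment and the retention through the wait.

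Fifth, the plan allows other covariates. These do not fill the gap: the baseline-difference rule cannot pick up differences that arise during the wait, and individual characteristics do not include arm.

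A reader might infer that the pooled effect size is biased. The documents do not support that. An average over two randomised timing groups is a legitimate summary, and the pooled model uses a report taken just before the FMI.

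**Conclusion.** The pooled models lack an arm and an arm-by-time term, and no other part of the plan supplies them. The consequence is conditional. With no arm difference in change there is none. With differences of 0.3–0.5 SD in both constructs the arm-driven correlation is 0.02–0.06; only at about 0.8 SD (0.14, with roughly a quarter of null tests falsely positive) does it become serious. These figures assume equal arms, total slopes treated as observed without error, and arm differences that the documents do not quantify. Correlations that involve intercepts are open to the same effect if the arms differ in level.

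It would be going too far to say that the trial's treatment comparison is compromised: the between-group models carry a treatment term and are not affected. It would also be going too far to say that the mechanism correlations are spurious, or that an arm-by-time term would confirm replication in the delayed group. With a half-width of 0.40–0.51 SD it could do neither. The case for the change is that it removes an avoidable ambiguity from the analysis of a primary goal at almost no cost.

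**What to change.** In the SAP and in protocol section 16.1:

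- Add randomised arm (immediate versus delayed FMI), effect-coded or centred, and arm-by-time as dyad-level fixed effects in every pooled growth model. Centring keeps the time coefficient as the average change.
- Report change by arm with 95% confidence intervals beside the pooled value.
- Relate slopes across constructs adjusted for arm, using either random-effect slopes from the arm-adjusted model or slopes centred within arm, not both. State whether the slopes are person totals or deviations from the dyad. Use the same slopes in the victimization model.
- State that the arm-by-time estimate is descriptive and will not be used as a test that permits pooling or shows replication.

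The cost is SAP wording and about 2 of the 47 degrees of freedom between 48 dyads. No new data are needed, and the larger sample that motivated pooling is kept.

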**Stage 3: Intervention Testing**

**Aim 3.** Conduct a mini-trial with 3-month follow-up via weekly assessments to examine changes in target attitudes (readiness, barriers) and behaviors (friend-based assault prevention behavior skills). We also will examine knowledge and strategies pertaining to the role of alcohol in helping behavior, and will test whether drinking influences the implementation and efficacy of this intervention.

Twenty-four friend dyads will participate in the FMI along with 24 wait-list control dyads (total of 48 dyads). We will compare groups on outcomes at post-intervention and at bi-weekly 3 month follow-ups, and also examine within subjects change. Given the pilot nature of the R34 mechanism and the smaller sample size, we will focus on whether effects are in the expected direction and whether the strength of effect sizes are of practical magnitude. We expect participants receiving the FMI to demonstrate significant increases in readiness, and engagement in FAPBs and alcohol strategies, and decreases in perceived barriers (improved self-efficacy, relationship concerns), at post-intervention and over the 3-month follow-up. We will also use our follow-up data to provide a rich description of the role of alcohol in implementing FAPBs, and whether the FMI reduces the impact of alcohol use. In exploratory analyses, we will examine whether the intervention may be associated with decreased assault risk, as well as decreased drinking (see **Data Analysis Plan**).

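### The combined-group change model gives each woman one slope through baseline and six follow-ups, which cannot represent a jump after the single FMI session

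*Combined protocol and SAP*

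**What the plan says.** The model in question is the combined-group change model in the SAP's outcome analyses. It pools post-intervention data from both arms once the waitlist dyads have also had the FMI and been followed up.

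- The series starts with "reports of past week protective behavioral strategies just prior to the intervention" and adds the follow-up records, "yielding 7 repeated measures nested within individuals and individuals nested within dyads".
- On time the SAP says only "Time will be included as a level-1 covariate". The matching text in protocol section 16.1 speaks of growth models and gives no functional form. Neither names a step, piecewise, quadratic or categorical term.
- One intercept and one slope per woman are then output. They are correlated with each other (the mechanism question, Aim 3 goal 3). The same models are used to relate individual characteristics to change. The exploratory victimization model takes the FAPB intercepts and slopes as predictors, with the reading that "Steeper increases in FAPBs are expected to be associated with lower likelihood of sexual victimization".

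On the intervention, Stage 3 Procedures state that "The FMI will consist of a single session". Stage 3: Intervention Testing expects the changes "at post-intervention and over the 3-month follow-up".

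**The concern.** The only exposure falls between the first and second of the seven records, and the plan expects a response by the second. The expected course is a jump, followed by holding, fading or further growth. A straight line from the pre-intervention record to week 12 describes something else, a steady rise from baseline.

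The line responds to a jump in two ways. It raises the fitted baseline, and it spreads the rest of the gain over 12 weeks. The individual intercept then holds part of the response, and the individual slope is no longer a clean measure of it. If the gain fades, the slope shrinks and can change sign even though every follow-up is above baseline. These two quantities are what the plan carries into goal 3, the moderator analyses and the victimization model, where a steeper slope is read as more benefit.

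**Working it through.** **Inputs.** One pre-intervention record and seven in all (SAP). Follow-up: "We will conduct bi-weekly online post-intervention assessments" for 12 weeks, with "the first assessment to occur within 2 weeks of FMI completion" (Stage 3 Procedures). One session.

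**The plan's own figure.** 1 + 12/2 = 7 records, as stated. Weekly records would give 1 + 12 = 13, so the count fits only the bi-weekly schedule.

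**Set-up.** Number the records t = 0, 1, ..., 6 (weeks 0, 2, ..., 12). The mean of t is 3 and the sum of (t − 3)² is 28. Scale the true baseline to 0 and the immediate gain to 1. Let the gain fade linearly to a fraction r at week 12; r = 1 means fully kept. The values of r are assumptions. With complete, balanced data the least-squares line below is also the average slope of a random-intercept, random-slope model.

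**Formulas.**
- For r = 1, the sum of (t − 3)y is −2 − 1 + 0 + 1 + 2 + 3 = 3. Linear fading subtracts 25(1 − r)/5 = 5(1 − r).
- Slope per two weeks = (5r − 2)/28, and fitted 12-week change = 6 × slope.
- Fitted baseline = (3 + 3r)/7 − 3 × slope = (18 − 3r)/28.
- True mean follow-up gain = (1 + r)/2.

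| r | Slope per 2 weeks | Fitted 12-week change | Fitted baseline (true 0) | Mean follow-up gain |
|---|---|---|---|---|
| 1.0 | 0.107 | 0.64 | 0.54 | 1.00 |
| 0.8 | 0.071 | 0.43 | 0.56 | 0.90 |
| 0.5 | 0.018 | 0.11 | 0.59 | 0.75 |
| 0.4 | 0.000 | 0.00 | 0.60 | 0.70 |
| 0.3 | −0.018 | −0.11 | 0.61 | 0.65 |
| 0.0 | −0.071 | −0.43 | 0.64 | 0.50 |

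The slope is zero at 5r = 2, that is r = 0.4. If the first follow-up is at week 1 and the rest are evenly spaced to week 12, the threshold is 47%. With exponential fading the slope is negative for a half-life of 4 weeks (−0.047) or 6 weeks (−0.020) and about zero at 8 weeks.

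**Comparison of courses.** A woman who rises steadily to 1 at week 12 has slope 1/6 = 0.167 and mean follow-up gain 0.583. A woman who gains 1 at once and keeps it has slope 0.107 and mean gain 1.000. The slope puts the first ahead.

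**Slope and true response.** In a simulation of 48 dyads (2,000 runs), the assumed values were mean gain 0.6 with SD 0.5 and negative draws set to zero, residual SD 0.6, dyad SD 0.5 and person SD 0.6. The correlation of individual slope with true gain was +0.39 when the gain was kept, +0.07 at fading to 50%, −0.14 at 20% and −0.27 at zero.

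**A step plus a post-session slope, same data.** A kept gain returns step 1.000 and slope 0.000. Fading to zero returns 1.000 and −0.200 per two weeks. A 4-week half-life returns 0.900 and −0.161.

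For perceived barriers, where benefit is a decrease, the signs reverse.

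**The case against.** Five arguments have weight.

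1. The SAP does not use the word linear for time. That is correct. A straight line is an inference from one time covariate and one slope per woman. If another form is meant, the SAP should state it.

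2. The immediate response is measured elsewhere. The SAP compares FMI with waitlist at the first post-intervention assessment and over the six follow-ups, and it reports baseline-to-first and baseline-to-last effect sizes. This stands: goals 1 and 2 do not use the combined-group slope. A reader might infer that the trial's estimates of the FMI effect are distorted, and the documents do not support that. But the SAP does not carry these results into goal 3, the moderator analyses or the victimization model.

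3. Intercepts are carried forward too, and they absorb part of the jump. This stands in part. With assumed gain SD 0.5, person-level SD 0.78 and residual SD 0.6, at fading to 50% the slope alone correlates 0.08 with true gain, and intercept and slope together reach 0.37. With the intercept in the model, the slope's coefficient is still positive at 30% retention and turns negative by 20%. But the intercept then mixes baseline level with response, so neither coefficient can be read as the plan reads it.

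4. A reader might infer that the mechanism correlations would rank responders wrongly. That does not follow. If two constructs share a time shape, each slope is the same multiple c of the woman's gain, so their covariance is c² times the covariance of the gains. The sign is preserved, and the cost is attenuation, to nothing where c = 0 (r = 0.4). Reversal needs constructs with different shapes.

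5. A negative slope needs strong fading. No fade rate is given, and women are encouraged to use the skills for 12 weeks. At 80% retention the fitted 12-week change is clearly positive, at 0.43.

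The victimization model is also labelled exploratory, which limits the consequence there. Goal 3 is listed among the primary goals of Aim 3.

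**Conclusion.** The point holds for the combined-group change model and the analyses that use its individual slopes and intercepts. Read as a straight line, the model cannot represent the jump that the design leads one to expect. With no fading at all, it reports 0.64 of a kept gain as 12-week change and puts 0.54 of it into the fitted baseline. With fading, the slope's relation to true response weakens, and under strong fading it can reverse. For linear fading with the first follow-up at week 2, the average slope turns negative below 40% retention at week 12.

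The misfit to a jump needs only the straight-line reading and an immediate response. The sign change also needs an assumed fade. The documents do not support a forecast that slopes will be negative in this trial. The correction should be made because it uses data already being collected and bears on a stated goal.

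**What to change.** State the form of time in the SAP for the combined-group model:

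- a step, coded 0 for the pre-intervention record and 1 for all follow-ups;
- linear time counted from the first follow-up, set to 0 for the pre-intervention record;
- a random step at the woman level, since a fixed step alone gives no individual value to carry forward.

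Use both the step and the post-session slope in the goal 3 correlations, the moderator analyses and the victimization model, and reword the directional expectation for victimization to match.

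Name a fallback in advance. If the random step does not converge, use each woman's baseline-to-first-follow-up difference, which the SAP already computes for an effect size, or her mean follow-up minus baseline.

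The cost is SAP wording and one more random effect. There are no new data. The drawback is noise, because each woman's step rests on a single pre-intervention record. With independent residuals of variance σ², a woman's own least-squares step has error variance σ²(1 + 1/6 + 2.5²/17.5) = 1.52σ². The first-follow-up difference has 2σ², and mean follow-up minus baseline has 1.17σ². At the assumed residual SD of 0.6 these are error SDs of 0.74, 0.85 and 0.65, against an assumed SD of true gains of 0.5. Individual steps should therefore be reported as imprecise, in line with the plan's focus on effect sizes with 95% bands.
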